5 STATISTICAL METHODOLOGY

5.1 Detailed power and sample size

The aim of the study is to demonstrate the non-inferiority of T2259 with regard to Vismed® Multi in terms of performance. The primary performance criterion is the change from baseline of total ocular staining grade in the worst eye on Day 35, evaluated using Oxford 0-15 grading scheme.

As the statistical hypothesis is the non-inferiority of T2259 with regard to Vismed®, the main analysis of the primary criterion will be performed in the Per Protocol population.

A total of 76 patients (i.e. 38 per treatment group) assume at least 90% power to establish the non-inferiority comparison on a one sided two sample t test with $\alpha=2.5\%$ basis (equivalent to a 95% two sided confidence interval), assuming that the standard deviation is 2.5 and no difference between the 2 groups with a non-inferiority limit set at 2 for the change in total ocular staining grade.

Estimation of the standard deviation and determination of the non-inferiority limit are based upon data of previous studies and literature.

Concerning the non-inferiority limit, according to clinicians, a variation of 2 points in the total Oxford grade, which corresponds to a variation of less than 1 grade in the three areas (corneal, temporal and nasal), is considered as not clinically significant.

For taking into account approximately 15% of patients non-evaluable in Per protocol analysis (premature withdrawals without performance evaluation, patients with major protocol deviation), a total of 90 patients should be randomised in the study.

The non-evaluable patient rate was based on the previous studies major deviations and missing data. For this study, missing data are higher than planned (partially due to Covid-19 pandemic) and the number of randomised patients is 101 to maintain approximately the number of 76 patients evaluable in the Per Protocol.

5.2 Generalities for statistical analyses

After the database lock and the randomisation code release, the statistical analysis will be performed by the statistician of Axonal-Biostatem, using SAS® software v9.4 (GUIDE, SAS Institute, North Carolina, USA), according to this SAP.

Disposition and baseline characteristics will be presented overall (globally) and by treatment groups. Performance and safety assessments and exposure/compliance will be presented by treatment groups.

Continuous variables will be summarised using descriptive statistics (number of non-missing data (n), number of missing observations, mean, standard deviation (SD), median, lower quartile (Q1), upper quartile (Q3), minimum and maximum).

Except minimum and maximum, descriptive statistics will be presented with one more decimal than the recorded value.

To compare treatment groups for ordinal qualitative variables, Cochran-Mantel-Haenszel (CMH) test will be used stratified by baseline values (if mentioned), with modified ridit scores and “row mean score differ” option. To compare treatment group when variable will be quantitative, Student T-test will be used, when data distribution will be assumed as normal (Shapiro-Wilk test for normality). If it is not the case, Mann-Whitney Wilcoxon test will be preferred instead.

Quantitative parameters will be also compared between groups using ANCOVA model. Furthermore, the mean change from baseline in total staining grade in the worst eye at Day 35 will be compared between the two treatments based on the MMRM analysis, which assumes:

- Data are Missing At Random (MAR)
- All the available data provide the information about non-observed data
- The treatment effect assume that the withdrawn patients mimic those who continued

Assumptions underlying the ANCOVA (respectively MMRM for the sensitivity analysis) will be checked:

- A histogram of residuals will be plotted to check the assumption of normality
- The underlying assumptions of normality of residuals will also be checked by using Shapiro-Wilk test
- Normal probability plot and QQ-plot will be performed to check the assumption of normality
- Residuals will be plotted against predicted values to check the assumption of heteroscedasticity
- For ANCOVA models, Levene's test will also be performed to check the homogeneity of variances

For each model (MMRM or ANCOVA) if there is a strong violation of normality assumption, a non-parametric comparison – Wilcoxon Rank Sum Test – will be performed in addition to the initial model.

Frequency distribution (number of non-missing observations (n), count and percentage of each modality,) will be summarized for the categorical variables.

All percentages should be rounded and reported to a single decimal place (xx.x%).

For all variables, the number of missing values will also be reported in the tables, but they will not be counted for the percentage calculation (categorical data).

Assessment recorded for both eyes will be presented for the worst eye and for the contralateral eye.

Baseline will be defined as the last value before the first instillation.

Change from baseline is defined as the change from the last assessment before the first instillation of the IMD.

However, if measurements are repeated before and after each instillation, baseline is defined as the assessment before the concerned instillation. In this case, the changes from baseline are defined from values assessed after the IMD intake minus the baseline values (last assessment before concerned IMD).

Time between two dates will be calculated as latest date minus earliest date. Study days prior to first injection date are calculated as (actual date – first injection date), after first injection date as (actual date – first injection date) + 1.

All patient data listings will be edited separately. The subject ID, the concerned eye (Right eye/Left eye), the worst eye (Right eye/Left eye), the treatment group, the visit (if applicable) will be presented as identifier variables. Analysis populations for each patient will appear in all the listings.

All patient data listings described in Section 11.9.2 of Clinical Investigation Report will be edited for all the recorded assessments and derived data by type of parameters: Disposition, Demography, Medical history, Previous and Concomitant treatments, Other baseline characteristics (all assessments recorded only at baseline), Performance assessments and endpoints, Safety examinations – by visit, Adverse event, exposure to treatments (Hydrabak®, T2259, Vismed® Multi), Compliance.

Data listings will be presented sorted by subject ID, eye (if applicable) and timepoint (visit).

All date fields will be presented in a format of ddmmmyyyy (e.g., 01Jan2004) in the listings.

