5.4 Adjustments for Covariates

For the primary analysis, ANCOVA model will be constructed including investigation product as factor and Oxford total score at baseline (Day1) as continuous covariate.

Country and the investigation product-by country interaction will be in addition explored as a secondary analysis prior to presenting the final model.

Moreover, for the primary endpoint, in MMRM analysis (sensitivity analysis), investigation product, Oxford total score at baseline (Day1), visit, investigation product by visit interaction and Oxford total score at baseline by visit interaction will be in the model.

As sensitivity analysis, for the primary endpoint, possible impact of COVID-19 and investigation product by possible impact of COVID-19 will be added in the ANCOVA model.

There is a single primary performance endpoint in the study (change from baseline in the ocular staining grade at D35 in the worst eye) and non-inferiority will be concluded if it is achieved. Other performance endpoints are defined to be of secondary importance. Thus comparison will be performed at a two-sided significant level of 5% and no adjustment of the type I error will be made.

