6.7 Performance analyses

6.7.1 Primary Performance Endpoint

Primary performance endpoint will be analysed only in the worst eye.

Descriptive tables will be produced presenting selection, baseline (D1), Day 8, Day 35 and Day 84 Oxford Total score and change from baseline for Oxford Total score at Day 8, Day 35 and Day 84.

Oxford grade at each visit and change from baseline at Day 8, Day 35 and Day 84 will be also described for each panel: temporal bulbar conjunctiva, corneal area and nasal bulbar conjunctiva.

The hypothesis of non-inferiority of T2259 compared to Vismed® Multi will be tested by calculating the bilateral 95% CI of the difference between groups (T2259 – Vismed® Multi) of the change from baseline of Oxford Total Score on Day 35. A two-way analysis of covariance (ANCOVA) model will be constructed using main effects of investigation product and baseline score as covariate. Adjusted means by investigation product will be presented as well as an estimate of the difference between adjusted means.

A 95% two-sided confidence interval, based on the ANCOVA model (2), will be computed for the difference of T2259 minus Vismed® Multi. If the upper bound is no higher than 2 points for the PP population, it will be concluded that the null hypothesis can be rejected and that T2259 is non-inferior to Vismed® Multi.

The result will be presented as follow:

Population	T2259 (N=XX)	Vismed® Multi (N=XX)	Difference T2259 – Vismed Multi	SE of Difference T2259 – Vismed Multi	95% CI
Day 1 (baseline) mean (SD)	X1	Y1			
Day 35 mean (SD)	X2	Y2			
Adjusted mean change (SE) between Day 1 and Day 35	[X2- X1]*(SE)	[Y2-Y1]*(SE)	[X2-X1] -[Y2-Y1]	SE	[Min - Max**]

* These values were expected as negative, meaning an improvement of the Oxford score.

** The upper bound indicates the maximal difference of change in disfavour of T2259.

This analysis will be performed firstly on the Per Protocol population on the observed data.

Same analysis will be performed on FAS population with imputation of values in case of missing data with LOCF technique (Day 8 or value in case of withdrawal) and without imputation (observed cases) for confirmation.

The country and the investigation product-by-country interaction will be explored as a secondary analysis prior to presenting the final model (1).

Same analysis as principal analysis (ANCOVA model) will be performed adjusted on possible impact of COVID-19 pandemic (3).

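### For the primary endpoint, the Wilcoxon back-up in SAP 5.2 tests for no difference rather than against the 2-point margin, so it cannot check the non-inferiority conclusion

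*SAP*

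**What the plan says.** The primary question is a margin question. SAP 6.7.1 states: "The hypothesis of non-inferiority of T2259 compared to Vismed® Multi will be tested by calculating the bilateral 95% CI" of the between-group difference in Day 35 change. The interval comes from one named model: "A 95% two-sided confidence interval, based on the ANCOVA model (2), will be computed for the difference of T2259 minus Vismed® Multi". The rule is "If the upper bound is no higher than 2 points for the PP population, it will be concluded that the null hypothesis can be rejected", with confirmation in the FAS. SAP 5.1 gives the margin and the planning assumptions: "with a non-inferiority limit set at 2 for the change in total ocular staining grade", "assuming that the standard deviation is 2.5 and no difference between the 2 groups".

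The back-up is in SAP 5.2. It is a general rule: "For each model (MMRM or ANCOVA) if there is a strong violation of normality assumption", then "a non-parametric comparison – Wilcoxon Rank Sum Test – will be performed in addition to the initial model". The section lists diagnostics (histogram, normal probability and QQ plots, Shapiro-Wilk test) but sets no threshold for a strong violation. It gives no shift by the margin, no interval, no covariate and no statement of how the rank-sum result will be read. SAP 6.7.1 and the planned primary-endpoint tables (5.1 to 5.6 in SAP 8.1) add none of these.

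**The concern.** A rank-sum test of no difference asks whether the two arms differ at all. The trial asks whether any T2259 disadvantage is smaller than 2 points. A large p-value against zero does not show that the deficit is below 2, and a small one does not show that it reaches 2. The test also drops the baseline Oxford score, which the primary model includes.

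All the other planned analyses of the primary endpoint (the country and COVID-19 ANCOVAs, the FAS repeats and the MMRM) are normal-theory linear models. The Wilcoxon test is the only one that does not assume normality. If the diagnostics raise doubt, it is therefore the only planned analysis that could say whether the conclusion is robust, and it addresses a different hypothesis.

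**Working it through.** **Inputs** (SAP 5.1): margin 2, SD 2.5, one-sided alpha 2.5% (two-sided 95% CI), 38 evaluable per arm, planned true difference 0.

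**The plan's own figure.** Standard error of the difference = 2.5 × √(2/38) = 0.574. Noncentrality = 2/0.574 = 3.49 on 74 df, which gives 93.1% power by the t-test. This agrees with the stated minimum of 90%. Randomised number: 76/(1 − 0.15) = 89.4, rounded up to 90, as stated.

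**Why the two questions differ.** The expected 95% CI half-width is t(0.975, 74 df) × 0.574 = 1.14.
- Non-inferiority needs an observed difference of at most about 2 − 1.14 = 0.86.
- A test against zero stays non-significant up to about 1.14.
- Between 0.86 and 1.14 there is no significant difference, yet non-inferiority is not shown.

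**Normal data.** Simulation with 20,000 trials per row, 38 per arm, normal changes, no baseline adjustment. The CI rule is the unadjusted t-based interval.

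| True T2259 deficit | Wilcoxon non-significant | CI rule shows non-inferiority | Non-significant, CI rule fails | Rank test shifted by 2 shows non-inferiority |
|---|---|---|---|---|
| 0 | 95.4% | 93.1% | 4.7% | 91.9% |
| 1.0 | 60.8% | 40.2% | 21.2% | 38.5% |
| 1.5 | 29.2% | 13.5% | 16.0% | 12.9% |
| 2.0 | 8.1% | 2.4% | 5.9% | 2.4% |

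Rounding the changes to whole points moved these results by at most about 1 percentage point. At a deficit of 1.0, 21.2/60.8 = 35% of the non-significant Wilcoxon results come from trials that did not show non-inferiority. At 1.5 it is 16.0/29.2 = 55%.

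**Skewed data.** With exponential errors at the same sample size, and a true deficit of 1.0 (half the margin), the ordinary Wilcoxon test is significant against T2259 in about 73% of trials. The rank test shifted by 2 shows non-inferiority in about 72%. Since 73% + 72% − 100% = 45%, at least about 45% of such trials give both results at once: significantly worse than the comparator, and non-inferior within the margin. Here the planned back-up would seem to contradict a conclusion that a margin-based check supports.

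**A margin-based check is feasible.** The shifted rank test, one-sided at 2.5%, has about 92% power at no difference (91.9% continuous, 91.5% rounded) and about 2.4% type I error at a deficit of 2.

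**The case against.** There are four points on the other side.

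- **The test decides nothing.** It is conditional and additional. SAP 5.4 ties the conclusion to the single primary endpoint: "non-inferiority will be concluded if it is achieved". No Wilcoxon p-value can alter the ANCOVA interval. This stands, and it limits the point to a supplementary analysis.
- **The primary interval is probably robust.** The planned ANCOVA rule was simulated with integer changes, error SD 2.5, baseline 4 to 9 and an assumed baseline slope of −0.3. At a true deficit of 2 it gave false non-inferiority in 2.4% of trials under exponential, reversed exponential, lognormal and t (3 df) errors, and 2.6% under normal errors. Power at no difference was 91% to 93%. This stands where both arms share the error distribution. It supports the ANCOVA, but does not make the Wilcoxon test a check of the margin.
- **Normal-data figures describe a case where the test would seldom be run.** This is fair. The table shows that the hypotheses differ, not how often the trial would be misled. The exponential case is closer to the situation that triggers the test, and there the mismatch takes the opposite form.
- **The rule is general.** SAP 6.7.2 plans two-sided p-values for differences in secondary endpoints, and a rank-sum test of difference suits those. This stands.

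A reader might infer that the sponsor intends to present a non-significant Wilcoxon result as support for non-inferiority. The documents do not say so; they are silent on interpretation. Nor is the rank-sum method itself incapable of addressing a margin. Only the test as specified lacks the link.

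**Conclusion.** The point holds for the primary endpoint. As specified, the back-up is an unadjusted test of no difference and cannot confirm or question the conclusion about the 2-point margin. Depending on the shape of the data, it can look reassuring when non-inferiority is not shown (about 21% of trials at a deficit of 1.0, normal data) or alarming when the deficit is half the margin (significant in about 73%, exponential errors).

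These sizes assume 38 per arm, SD 2.5, no baseline adjustment and the same distribution in both arms apart from a shift. The documents give no information on the actual distribution of changes. No error in the primary decision rule is shown, and the available simulations suggest that the ANCOVA interval keeps its error rate under shared non-normal errors. The defect is a supplementary analysis aimed at the wrong hypothesis. It should be corrected, but it does not threaten the primary result.

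**What to change.** In SAP 5.2, exempt the primary endpoint from the Wilcoxon rule, and in SAP 6.7.1 specify one margin-based check:

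1. **Preferred:** a bootstrap 95% CI for the ANCOVA-adjusted difference (T2259 minus Vismed Multi), judged by the same upper-limit rule of 2 points. It keeps the baseline adjustment and the scale of the primary analysis. Its operating characteristics were not simulated here.
2. **Alternative:** a one-sided 2.5% rank-sum test after subtracting 2 from each T2259 change. State that it is unadjusted and that it addresses the 2-point margin only under a location shift.

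A Hodges-Lehmann interval is not recommended. Its limits fall on whole points for this score. Accepting an upper limit of 2 or less passed about 12% to 13% of simulated trials at a true deficit of 2, and requiring a limit strictly below 2 reduced power at no difference to about 71%.

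Add one sentence that a non-significant test of difference is not evidence of non-inferiority. Keep the ordinary Wilcoxon test for secondary endpoints. The cost is SAP wording and slight extra programming; no further data are needed, and the primary analysis and its power do not change.

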5.3 Multiple Imputations for Handling of Dropouts or Missing data

Treatment Emergent Adverse Events (TEAEs) are AEs that occurred after the first IMD instillation. AEs that occurred the day of the first IMD instillation will be reviewed in detail to identify if AEs appeared before or after the first treatment with IMD (to decide if they have to be considered as TEAEs or not). If no additional information is available, they will be treated as TEAEs.

By default, AEs will be considered as TEAEs if no enough information is available.

For primary analysis performed on FAS, Last Observation Carried Forward (LOCF) method will be applied in case of missing value.

In order to define the type of treatments (previous, concomitant or post-study) and treatment duration, partially start/end dates will be imputed with the following rules for calculations:

For treatment start date:

- If only the day is missing, it will be considered as 1st for calculations
- If only the year is completed, day and month will be considered as January 1st for calculations

For treatment end date:

- If only the day is missing, it will be considered as the last day of the month for calculations
- If only the year is completed, day and month will be considered as December 31st for calculations

If the date is totally missing, it will not be replaced.

Other missing data will not be replaced.

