Statistical method	
The aim of the study is to demonstrate the non - inferiority of T2259 with regard to Vismed® Multi in terms of performance.
 
The primary performance criterion is the change from baseline of total ocular staining grade in the worst eye on Day 35, evaluated using Oxford 0-15 grading scheme.
 
As the statistical hypothesis is the non-inferiority of T2259 with regard to Vismed® Multi, the main analysis of the primary criterion will be performed in the Per protocol population.
 
A total of 76 patients (i.e. 38 per treatment group) assume at least 90% power to establish the non-inferiority comparison on a one-sided two sample t-test with alpha=2.5 % basis (equivalent to a 95% two-sided confidence interval), assuming that the standard deviation is 2.5 and no difference between the 2 groups with a non-inferiority limit set at 2 for the change in total ocular staining grade.
 
Estimation of the standard deviation and determination of the non-inferiority limit are based upon data of previous studies and literature.
 
Concerning the non - inferiority limit, according to clinicians, a variation of 2 points in the total Oxford grade, which corresponds to a variation of less than 1 grade in the three areas (corneal, temporal and nasal), is considered as not clinically significant.
 
For taking into account approximately 15% of patients non-evaluable in Per protocol analysis (premature withdrawals without performance evaluation, patients with major protocol deviation), a total of 90 patients should be randomised in the study.

Sample size	90 randomised patients.										
Investigation Design	Multicentre, randomised study, investigator-masked, 2 parallel groups (T2259 versus Vismed® Multi) of 38 evaluable patients each.										
Investigation Duration	Run-in-period with preservative free artificial tears (Hydrabak®): from Day 1-10 or Day 1-7 to randomisation visit (Day 1) (one drop in each eye 3 to 6 times daily). 
 ▪ Treatment period: 84 ± 7 days ▪ Total study duration: maximum of 101 days 										

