2 STUDY DESIGN

2.1 Overview

This is a multicentre, randomised study, investigator-masked, 2 parallel groups (T2259 versus Vismed® Multi) of 38 evaluable patients each.

The patients were randomised after a run-in-period of 7 to 10 days with preservative free artificial tears (Hydrabak®, one drop in each eye 3 to 6 times daily). Then, they were treated with either T2259 or the reference product (Vismed® Multi) for 84 days (\pm 7 days).

Investigation visits were performed as following:

Day 1-10/Day 1-7	Selection visit (Visit 1)
Day 1	Randomisation/ Inclusion visit (Visit 2)
Day 8 (\pm 1)	Visit 3 Optional Visit (if the investigator and/or the patient thinks it is necessary)
Day 35 (\pm 3)	Visit 4
Day 84 (\pm 7)	Final visit (Visit 5)

The Visits V2, V3, V4 and V5 should have been performed at the same hour (± 4 hours).

Reclassification of visits:

All “premature withdrawal” visits will be reclassified as decided in BR Meeting. Number of days between premature withdrawal visits and randomisation visit will be calculated and depending of this number of days, visits will be reclassified to the nearest planned non-missing visit.

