2.4 Randomisation

A patient who had given his/her written informed consent and who was included in the study was assigned a specific treatment number.

Random allocation of patients in the T2259 group or Vismed® Multi group assure that all patient's known and unknown characteristics are similar and balanced between groups at the beginning of the study, avoiding the selection bias.

The randomisation code list stratified by site was generated by the CRO in charge of the statistics (AXONAL-BIOSTATEM / independant statistician). Patients were randomised on a 1:1 basis to T2259 or comparator product respectively. The Investigational Medical Device (IMD) was allocated to the patients according to randomisation using an interactive response system (IWRS).

Randomisation occurred at the randomisation visit (Day 1; Visit 2) after all screening procedures had been performed and eligibility for the study confirmed. The patient who met the eligibility criteria was randomly assigned to treatment and associated to a randomisation number.

The treatment number should be recorded in patient's source documents and in the e-CRF.

During the visit 4 (Day 35), this investigator allocated the same treatment number than he did at the randomisation visit.

The treatment number must be recorded in the patient's source document and the e-CRF.

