Table 5.6b: Results of MMRM analysis in change from baseline in Oxford total score at D35 – Worst eye – FAS population

Table 5.6c: Results of MMRM analysis in change from baseline in Oxford total score at D35 – Worst eye – with LOCF imputation — FAS population

Secondary performance endpoints:

Table 5.7a: Results of ANCOVA analysis in change from baseline in Oxford total score at D8 and D84 – Worst eye – PP population

Table 5.7b: Results of ANCOVA analysis in change from baseline in Oxford total score at D8 and D84 – Worst eye – FAS population

Table 5.8a: Oxford total score at each timepoint and change from baseline – Contralateral eye – PP population

Table 5.8b: Oxford total score at each timepoint and change from baseline – Contralateral eye – FAS population

Table 5.9a: Oxford grade by panel at each timepoint and change from baseline – Contralateral eye – PP population

Table 5.9b: Oxford grade by panel at each timepoint and change from baseline – Contralateral eye – FAS population

Table 5.10a: Results of ANCOVA analysis in change from baseline in Oxford total score at D8, D35 and D84 – Contralateral eye – PP population

Table 5.10b: Results of ANCOVA analysis in change from baseline in Oxford total score at D8, D35 and D84 – Contralateral eye – FAS population

Table 5.11a: Van Bijsterveld items at each timepoint – Worst eye – PP population

Table 5.11b: Van Bijsterveld items at each timepoint – Worst eye – FAS population

Table 5.12a: Van Bijsterveld total score at each timepoint and change from baseline – Worst eye – PP population

Table 5.12b: Van Bijsterveld total score at each timepoint and change from baseline – Worst eye – FAS population

Table 5.13a: Van Bijsterveld – Results of ANCOVA analysis in change from baseline in Van Bijsterveld total score at D8, D35 and D84 – Worst eye – PP population

Table 5.13b: Van Bijsterveld – Results of ANCOVA analysis in change from baseline in Van Bijsterveld total score at D8, D35 and D84 – Worst eye – FAS population

Table 5.14a: Van Bijsterveld items at each timepoint – Contralateral eye – PP population

Table 5.14b: Van Bijsterveld items at each timepoint – Contralateral eye – FAS population

Table 5.15a: Van Bijsterveld total score at each timepoint and change from baseline – Contralateral eye – PP population

Table 5.15b: Van Bijsterveld total score at each timepoint and change from baseline – Contralateral eye – FAS population

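### The FAS confirmation of non-inferiority is led by LOCF, which can bias the Day 35 difference in either direction; the observed-data MMRM already in the plan should confirm instead

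*SAP*

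**What the plan says.** - **Decision rule.** SAP 6.7.1 concludes non-inferiority if the upper 95% bound is no higher than 2 points in the PP set, analysed on observed data. SAP 1.1 and Protocol 5.2 require confirmation in the FAS.
- **FAS method.** SAP 5.3: "For primary analysis performed on FAS, Last Observation Carried Forward (LOCF) method will be applied in case of missing value". Although the title of that section refers to multiple imputation, LOCF is the only method it gives for the endpoint. Protocol 7.3.2 puts LOCF first on the FAS and observed cases second. SAP 6.7.1 lists both as confirmation.
- **What is carried.** SAP 6.7.1 imputes "with LOCF technique (Day 8 or value in case of withdrawal". SAP 2.1 describes the Day 8 visit as "Visit 3 Optional Visit (if the investigator and/or the patient thinks it is necessary".
- **Withdrawal visits.** SAP 2.1 moves them to the nearest planned visit that is not missing. SAP 4.3 and 6.2 move them to the closest planned visit that is missing.
- **MMRM.** SAP 4.3, 5.2 and 6.7.1 add an MMRM as a sensitivity analysis under a missing-at-random assumption. Table 5.6b reports it on the FAS. SAP 8.1 also lists "Table 5.6c: Results of MMRM analysis in change from baseline in Oxford total score at D35" in the worst eye, run on the FAS with LOCF imputation.
- **Disagreement.** Neither document says which FAS result counts as confirmation if LOCF and observed cases differ.

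**The concern.** The FAS result is the safeguard against selection in the PP set, so its lead analysis should not bring in an avoidable bias of its own. LOCF does so in four ways.

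1. It treats an earlier grade as the Day 35 grade. Protocol 6.1 describes a disease that fluctuates over the short term and chose 35 days as long enough to judge performance, so a one-week grade is a doubtful substitute.
2. Whether there is a Day 8 grade to carry depends on someone having thought a visit necessary. A patient with neither a Day 8 nor a withdrawal grade cannot be imputed at all.
3. A patient who missed Day 35 but attended Day 84 belongs to the FAS, yet the Day 84 grade contributes nothing to LOCF or to observed-case ANCOVA. The MMRM uses it.
4. Filled values enter the ANCOVA as if they had been observed. Table 5.6c then passes the same filled data to the MMRM, which restores the assumption that the MMRM is meant to avoid.

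Missing data are not a side issue: SAP 5.1 says they exceeded the plan and that 101 patients were randomised instead of 90.

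**Working it through.** **1. The plan's own figures.** The Protocol synopsis specifies a "one-sided two sample t-test with alpha=2.5 % basis". SAP 5.1 states "A total of 76 patients (i.e. 38 per treatment group) assume at least 90% power", "assuming that the standard deviation is 2.5 and no difference between the 2 groups with a non-inferiority limit set at 2". SAP 2.4: "Patients were randomised on a 1:1 basis to T2259 or comparator product respectively".

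- SE with 38 per arm = 2.5 × √(2/38) = 0.574. Power = Φ(2/0.574 − 1.96) = 93.7% by the normal formula and 93.1% by the noncentral t. At least 90% is correct (34 per arm would suffice by t).
- 76/0.85 = 89.4, rounded up to 90, which matches.
- 1 − 76/101 = 24.8% not evaluable in PP. This mixes missing data with major deviations, so it is not the share of the FAS that LOCF would fill. That share is not stated, and 5% to 25% is assumed below.

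**2. Effect of LOCF with balanced missingness.** Let m be the share carried forward from Day 8, d8 the Day 8 difference, and 2.0 the true Day 35 difference (the margin, so any non-inferiority finding is false). Missingness is taken as unrelated to outcome, and all 101 patients are kept in the SE.

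- Expected LOCF difference = 2(1 − m) + m × d8
- SE = 2.5 × √(2/50.5) = 0.4975
- False non-inferiority rate = Φ(−1.96 + (2 − expected difference)/0.4975)

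| m | d8 = 0.5: expected difference, rate | d8 = 1.0: expected difference, rate |
|---|---|---|
| 5% | 1.925, 3.5% | 1.95, 3.1% |
| 15% | 1.775, 6.6% | 1.85, 4.9% |
| 25% | 1.625, 11.4% | 1.75, 7.2% |

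With d8 = 2.0 the expected difference stays at 2.0 and the rate at 2.5% for every m. With d8 = 2.5 and m = 15%, the expected difference is 2.075 and the rate Φ(−1.96 − 0.075/0.4975) = 1.7%, so the bias is against T2259.

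**3. Unequal missingness.** Assume no true difference, with both arms improving from −1 at Day 8 to −3 at Day 35.

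- T2259 25% missing, Vismed Multi 5%: T2259 mean = 0.25(−1) + 0.75(−3) = −2.5; Vismed Multi mean = 0.05(−1) + 0.95(−3) = −2.9; LOCF difference = +0.40, against T2259.
- Reversed rates: −0.40, in favour of T2259.

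**4. Simulation check.** 20,000 runs, 45 per arm, SD 2.5 at both visits, correlation 0.6, missingness unrelated to outcome, unadjusted mean difference in place of ANCOVA.

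- True difference 2, 15% missing per arm: LOCF gave 7.8% false non-inferiority when the arms were equal at Day 8, 4.7% when d8 was 1.0 and 2.6% when d8 was 2.0.
- Observed cases gave 2.3% to 2.6% in every scenario with a true difference of 2.
- In the step 3 case with more T2259 loss, power was 82.8% with LOCF and 92.7% with observed cases. With the reverse imbalance it was 99.2% with LOCF.

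The MMRM itself was not simulated.

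**5. Is the MMRM ready to take over?** SAP 4.3 and the text of 6.7.1 include a treatment-by-baseline interaction. SAP 5.4 and the code in 6.7.1 include baseline-by-visit instead. The code declares VIS and TT, but its REPEATED and ESTIMATE statements refer to VISIT, and ESTIMATE also refers to TREATMENT. The intended model has to be settled first.

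**The case against.** A reader might infer that LOCF necessarily pulls the arms together and so tilts the trial toward non-inferiority. The documents do not support that. They give no Day 8 effect and no missingness by arm, and steps 2 and 3 show that the sign depends on both. If patients doing badly on T2259 were the ones who came early or withdrew, LOCF could penalise T2259.

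A reader might also take the 6.6% or 11.4% as the chance that the trial wrongly declares non-inferiority. That does not follow either. The decision rule uses PP observed data, which LOCF does not touch. The percentages belong to one supporting analysis taken alone. The 15% and 25% inputs resemble the PP non-evaluable rates, and the share carried may be well below them: only patients lacking Day 35 but holding a Day 8 or withdrawal grade are filled, and some withdrawal grades may be reclassified as Day 35 itself.

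It is also fair that observed-case ANCOVA (Table 5.4b) and an MMRM without LOCF (Table 5.6b) are already planned on the FAS, that LOCF is protocol-specified, and that the MMRM brings its own missing-at-random assumption and uses the same discretionary Day 8 data.

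These arguments limit the size of the point but do not remove it. LOCF still leads the confirmation, no rule covers disagreement between FAS results, and Table 5.6c adds nothing to Table 5.6b.

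**Conclusion.** The point stands as a weakness in the FAS confirmation, not in the primary decision rule. LOCF is an unreliable lead analysis because its bias cannot be signed in advance, while an analysis using all observed grades is already in the plan. If a disadvantage for T2259 emerges after Day 8 and missingness is balanced, the illustrated rate for FAS-LOCF alone runs from 3.1% to 11.4% against a nominal 2.5%. That range rests on assumed values for the Day 8 difference and the share carried, and on missingness unrelated to outcome. With equal differences at both visits there is no bias; with a larger early difference, or more T2259 loss while scores improve, the result can be too harsh on T2259. This should be corrected before unblinding, but it does not by itself undermine a PP conclusion.

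**What to change.** Before the randomisation code is released:

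1. In SAP 5.3 and 6.7.1, name the FAS MMRM on observed data (Day 35 contrast, Table 5.6b) as the analysis that confirms the PP result. Keep FAS LOCF and FAS observed-case ANCOVA as sensitivity analyses. Naming one analysis also settles what happens if they disagree.
2. Delete Table 5.6c.
3. Choose one interaction term for the MMRM, state it identically in SAP 4.3, 5.4, 6.7.1 and the code, and make the variable names in the code consistent.
4. Reconcile the withdrawal-visit rule in SAP 2.1 with SAP 4.3 and 6.2, since it decides which grades count as Day 35 and which are carried.
5. Record the change in SAP 4.3, which already lists departures from the protocol.

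The cost is SAP wording and a small programming correction; no new data are needed. The downsides are a documented departure from the protocol's LOCF statement after all 101 patients were randomised, and reliance on missing at random for the confirming analysis.
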